13.0 MEDICAL MONITORING

It is the responsibility of the investigators to oversee the safety of the study at their site. This safety monitoring will include careful assessment and appropriate reporting of adverse events, as noted above, as well as the construction and implementation of a site data and safety monitoring plan. Medical monitoring by an independent clinician, will include a regular assessment of the number and type of serious adverse events on a periodic basis.

13.1 Study Monitoring Plan

This study will be monitored by the investigators and sub-investigators, as appropriate. Such monitoring will include at least weekly meetings of the study team to review accrual, toxicity, SAEs. Dose escalations and study finding. In addition, the PI will ensure that data are completed in a timely manner and their designee will review the data for accuracy, completeness and integrity.

13.2 Auditing and Inspecting

The investigator will permit the Office of Human Research Affairs, UnitedHealth Group to review records, data and facilities at mutually agreeable times. This study will be audited on an as needed basis with a complete review occurring at completion of enrollment. If enrollment numbers are not met, audit will occur in alignment with being notified of closure of the trial.

14.0 SCHEDULE OF EVENTS

See appropriate *Process Flows* for **PATCH 2 (Sub-Study 1)** and **PATCH 3 (Sub-Study 2)**

15.0 MEASUREMENT OF EFFECT

15.1 Definitions

Evaluable for toxicity: All participants will be evaluable for toxicity from the time of their first treatment with HCQ or placebo through final assessment.

Evaluable for primary outcome: Participants who received at least one continuous week of HCQ will be evaluable for the primary outcome.

15.2 Response Criteria

PATCH 2 (Sub-Study 1): Measurement of SARS-CoV-2 positivity confirmed by an accepted testing method. Rate of hospitalization will be defined by a hospitalization occurring within 30 days of the date of participant enrollment.

PATCH 3 (Sub-Study 2): Rate of COVID-19 infection will be defined by measurement of SARS-CoV-2 identified by accepted testing methods.

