1.0 OBJECTIVES

1.1 Primary Objectives

PATCH 2 (Sub-Study 1): Rate of hospitalization

PATCH 3 (Sub-Study 2): Rate of COVID-19 infection (confirmed by accepted testing methods) over two months

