Coronaviruses are a large family of viruses that commonly infect many animals, including camels, cattle, cats, and are often found in bats as their zoonotic reservoir. While it is rare, animal coronaviruses can infect people and then spread between people, as had occurred with Middle East respiratory coronavirus (MERS-CoV) and severe acute respiratory coronavirus (SARS-CoV), and now the newly emerged coronavirus SARS-CoV-2 (also known as COVID-19). The SARS-CoV-2 virus is a betacoronavirus, like MERS-CoV and SARS-CoV. All three of these viruses have their origins in bats. While SARS-CoV and MERS-CoV exhibit significantly higher mortality than SARS-CoV-2, the ability to spread between humans is less than SARS-CoV-2. There is emerging evidence from Asia that patients can be highly contagious with one patient spreading viral particles to 87% of 15 sites within the patient's room. Virus can be shed in urine and feces as well as respiratory secretions increasing the likelihood that sick contacts and hospital staff will become infected (2). An epidemiological survey of 72,000 cases in China found an overall 3.8% infection rate in hospital workers, but a 68% infection rate of hospital workers in Wuhan at the epicenter of disease. This suggests that if low rates of infection are in a community, the likelihood of hospital workers contracting disease is low, but if there are a large number of cases then the likelihood of hospital workers contracting the disease is high (3). Patients above the age of 50 are more likely to die of this disease and the time from diagnosis to death can occur within one month despite access to high-level intensive care units (4). A high rate of intra-family transmission and rapid community transmission has been documented in Shenzhen China (5). Meanwhile a screen of compounds found that chloroquine prevented and eradicated established infection of SARS-CoV-2 virus in vitro. I was contacted by researchers in China who indicated that 8/10 coronavirus infected patients treated with chloroquine 500 mg daily cleared their virus. The hospital ran out of chloroquine, and they have had to turn to other means of treating the virus. We believe hydroxychloroquine is a safer drug than chloroquine and affords the ability to dose escalate to concentrations that we know are effective at blocking the lysosome in patients.

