16.0 STATISTICAL CONSIDERATIONS

16.1 Sample size calculation

Because we are uncertain about the outcome values for both control (placebo) and treatment (HCQ) arms of the study, we will use group-sequential methods, allowing us to stop early for both efficacy and futility. We conduct two interim analyses and a final analysis, after approximately 1/3, 2/3, and 100% of participants have completed.

PATCH 2 & 3 TRIAL

We will use the Hwang-Shih-DeCani alpha spending rules. Boundaries for efficacy and futility decisions are shown below. Futility boundaries are non-binding.

z-value Stage	Boundaries		Information Proportion
	Efficacy	Futility	
1	2.7819	-0.8235	0.3400
2	2.2653	0.4262	0.6800
3	1.6813	1.6813	1.0000

p-value Stage	Boundaries		Information Proportion
	Efficacy	Futility	
1	0.00270	0.79490	0.3400
2	0.01175	0.33497	0.6800
3	0.04636	0.04636	1.0000

PATCH 2 (Sub-Study 1), Home quarantined patients with COVID-19: We will assume the null hypothesis that in the placebo arm 70% will recover without requiring hospitalization. For the low dose HCQ cohort 95% of home quarantined patients recover without requiring hospitalization. We will continue to enroll and randomize patients at the time of testing 1:1 HCQ to control until we reach at least 100 patients with at least 50 in the low dose HCQ arm and at least 50 in the placebo arm who have tested positive COVID19. The one-sided z- test ($\alpha=.05$) will have an at least 90% power to detect a significant difference between the groups of greater than 25% between the population rates. We estimate we will need to enroll 500 patients at the time of testing to reach the 100 patients who test positive for COVID19.

The *hypothesis* will be tested with only patients who tested positive for COVID19 using a one-sided test, with a z-score corresponds to the log of the odds-ratio for recovery between the two groups. We will obtain the estimate of the odds ratio, and 95% CI, from logistic regression. As a secondary analysis, we will stratify the analysis, and obtain separate estimates of the odds-ratio by group. However, we are not powered to test the interaction for significance, and we do not expect significance within group.

Interim analysis: We will perform two interim analyses at 34% and 68% completion, testing for early efficacy or futility, using z-score boundaries that follow Hwang-Shih-DeCani alpha spending rules. Following those rules, we have 90% power using 100% of the sample, if scenario is true.

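### PATCH 2's primary event is hospitalisation alone, but Section 16.1 tests an undefined recovery, so a death without admission has no agreed place in the primary analysis

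*Combined protocol and SAP*

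**What the plan says.** Section 1.1 gives the primary objective as "PATCH 2 (Sub-Study 1): Rate of hospitalization". Section 15.2 makes it operational: "Rate of hospitalization will be defined by a hospitalization occurring within 30 days of the date of participant enrollment". Neither mentions death.

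Section 16.1 uses other words. The control assumption is that "in the placebo arm 70% will recover without requiring hospitalization". The alternative is "For the low dose HCQ cohort 95% of home quarantined patients recover without requiring hospitalization". The test statistic is a "z-score corresponds to the log of the odds-ratio for recovery between the two groups", computed in patients who tested positive. Recovery is not defined in any section.

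Death appears only as a safety matter: the serious adverse event criteria (Section 10.0), the reporting of deaths (10.3) and IRB notification (11.0). No section makes it a failure, a component of the endpoint or a competing event.

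**The concern.** A primary endpoint should classify every analysed patient in one way. Here the worst outcome can be classified in two. If 15.2 governs, a patient who dies at home after becoming evaluable sits with the patients who did well. If 16.1 governs and recovery means what it says, the same patient is a failure.

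Under 15.2, the comparison is tilted towards whichever arm has more deaths outside hospital. The setting makes the gap relevant. Participants are aged 50 to 75, quarantined at home and followed remotely. Section 2.1 says "Patients above the age of 50 are more likely to die of this disease" and adds that death can come within a month of diagnosis, which is about the length of the endpoint window.

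**Working it through.** **1. One patient, three rules.** Take a randomised, COVID-positive patient who dies within 30 days without admission.

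| Rule | Classification |
|---|---|
| 15.2, hospitalisation within 30 days | No event |
| 16.1, recovery read literally | Failure |
| 16.1, recovery read as not hospitalised | No event, as in 15.2 |
| 15.1, at least one continuous week of HCQ needed to be evaluable | Dropped if death comes in the first week |

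The 15.2 wording therefore scores the death favourably only if the patient was already evaluable. An earlier death is removed from the analysis. Neither route counts it as a failure.

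**2. The plan's own figure.** Inputs from Section 16.1: 50 per arm, 70% versus 95%, one-sided alpha 0.05, stated power at least 90%.

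Pooled z-test: [0.25·√50 − 1.645·√(2·0.825·0.175)] / √(0.70·0.30 + 0.95·0.05) = (1.768 − 0.884)/0.507 = 1.74, so power is 0.959.

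Wald test of the log odds ratio: ln(0.95/0.05) − ln(0.70/0.30) = 2.097. SE = √(1/35 + 1/15 + 1/47.5 + 1/2.5) = 0.719. The ratio is 2.919, so power is Φ(2.919 − 1.645) = 0.899.

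Simulation with the printed boundaries at 34%, 68% and 100% gives one-sided alpha 0.050 with non-binding futility. Power is 0.945 (pooled z) and 0.891 to 0.895 (log odds ratio). The stated power reproduces to within about a point, and the endpoint question does not alter it.

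**3. How many deaths matter.** With a placebo and b HCQ failures out of 50 each,

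z = {ln[(50−b)/b] − ln[(50−a)/a]} / √[1/a + 1/(50−a) + 1/b + 1/(50−b)].

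The final efficacy boundary is 1.6813. The design rates imply 15 placebo and 2.5 HCQ failures.

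| Failures, placebo vs HCQ | Wald z | Boundary crossed? |
|---|---|---|
| 15 vs 3 | 1.904/0.671 = 2.84 | Yes |
| 15 vs 7 | 0.968/0.511 = 1.89 | Yes |
| 15 vs 8 | 0.811/0.494 = 1.64 | No |

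The pooled z agrees: 1.93 at 15 vs 7 and 1.66 at 15 vs 8. From 15 vs 7, one HCQ death counted as a failure changes the decision. From 15 vs 3, four such deaths (none on placebo) still leave z at 1.89, and five are needed.

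**4. How often the data would be that close.** I summed binomial probabilities over all 50-per-arm outcomes in which one extra HCQ failure moves z below 1.6813, ignoring interim stopping. The chance is 3.6% (Wald) or 3.4% (pooled) if the true success rates are 70% and 95%. It is about 11% by either test if they are 70% and 86%. Such a death must also occur.

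**5. Power if death counts as a failure.** The documents give no rate of death without admission, so these rates are assumptions. All figures are fixed-sample, 50 per arm.

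| Assumed deaths without admission | Power, pooled z | Power, log odds ratio |
|---|---|---|
| None | 0.959 | 0.899 |
| 1% in each arm | 0.952 | 0.898 |
| 2% in each arm | 0.944 | 0.896 |
| 5% in each arm | 0.921 | 0.883 |
| 2% on HCQ only | 0.916 | 0.864 |
| 5% on HCQ only | 0.811 | 0.774 |

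Equal rates cost little. The last two rows lose power because the drug is then doing less good, which the analysis ought to show.

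**6. Whether deaths to Day 30 would be known.** Portal self-reporting ends after Day 14 (Section 4.0). Adverse event reporting ends at the last dose (9.2), and 10.3 ties death reporting to the adverse event period. After the study period, Section 10.0 asks only for serious events that are at least possibly related. The one later planned contact is the Day 29 to 31 test, and a missed test does not reveal why it was missed.

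**The case against.** The strongest reply is that recovery in 16.1 is simply loose wording for not hospitalised. The two sections would then agree, and the sponsor chose hospitalisation as its objective and reports deaths separately. This removes the contradiction but not the gap: under that reading, both sections leave an evaluable patient who dies unadmitted in the favourable group.

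Three stronger readings are tempting, and the documents do not support them.

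- A reader might infer that the plan declares death a success. It does not. Section 15.2 is silent, 16.1 can be read as scoring death as a failure, and 15.1 read literally drops first-week deaths.
- A reader might infer that one death overturns the trial. That holds only on a knife-edge such as 15 vs 7, where reclassifying any single HCQ patient as a failure would do the same. 7/50 is 86% success, not the 95% assumed.
- A reader might infer that cardiac deaths on HCQ would be counted as benefit, because Section 7.2 says the drug can prolong the QT interval. No rate or direction is given. The plan excludes several cardiac conditions and lists interacting drugs as exclusions. It has participants called three times a week and instructs them to call 911 for emergency symptoms. If unadmitted deaths fell mainly on placebo, the 15.2 wording would work against HCQ.

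**Conclusion.** The inconsistency is real and should be settled before the primary analysis. The primary outcome is worded in two ways, one of its terms is undefined, and death has no role in either wording. This rests on the text and not on a forecast of deaths.

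The likely numerical effect is small. Deaths without admission should be rare, and a single one matters only in a borderline result (roughly 3% to 4% of datasets under the design rates). The stated power stands. The size of any bias cannot be fixed from the documents, because it depends on an unstated death rate and on how the deaths divide between the arms.

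**What to change.** - In 15.2, define the PATCH 2 primary event as hospitalisation or death from any cause within 30 days of enrolment.
- In 16.1, use that event or its complement in place of recovery, for the assumed rates and for the test.
- Apply it to all randomised COVID-positive patients, so that the one-week rule in 15.1 does not drop early deaths.
- Report hospitalisation and death separately alongside the composite.
- Ascertain vital status and hospitalisation at 30 days from enrolment. For participants who miss the Day 29 to 31 test, use the alternate telephone numbers collected at registration (Section 4.0). Test days are counted from the first dose and the endpoint window from enrolment, so record dates and not only visit days.

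The cost is protocol and SAP wording, a small amount of follow-up calling and a slightly broader endpoint. No added patients are needed under equal assumed death rates of up to 5%: power falls by at most about 4 points with the pooled z (0.959 to 0.921) and under 2 points with the log odds ratio (0.899 to 0.883).

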16.0 STATISTICAL CONSIDERATIONS

16.1 Sample size calculation

Because we are uncertain about the outcome values for both control (placebo) and treatment (HCQ) arms of the study, we will use group-sequential methods, allowing us to stop early for both efficacy and futility. We conduct two interim analyses and a final analysis, after approximately 1/3, 2/3, and 100% of participants have completed.

PATCH 2 & 3 TRIAL

We will use the Hwang-Shih-DeCani alpha spending rules. Boundaries for efficacy and futility decisions are shown below. Futility boundaries are non-binding.

z-value Stage	Boundaries		Information Proportion
	Efficacy	Futility	
1	2.7819	-0.8235	0.3400
2	2.2653	0.4262	0.6800
3	1.6813	1.6813	1.0000

p-value Stage	Boundaries		Information Proportion
	Efficacy	Futility	
1	0.00270	0.79490	0.3400
2	0.01175	0.33497	0.6800
3	0.04636	0.04636	1.0000

PATCH 2 (Sub-Study 1), Home quarantined patients with COVID-19: We will assume the null hypothesis that in the placebo arm 70% will recover without requiring hospitalization. For the low dose HCQ cohort 95% of home quarantined patients recover without requiring hospitalization. We will continue to enroll and randomize patients at the time of testing 1:1 HCQ to control until we reach at least 100 patients with at least 50 in the low dose HCQ arm and at least 50 in the placebo arm who have tested positive COVID19. The one-sided z- test ($\alpha=.05$) will have an at least 90% power to detect a significant difference between the groups of greater than 25% between the population rates. We estimate we will need to enroll 500 patients at the time of testing to reach the 100 patients who test positive for COVID19.

The *hypothesis* will be tested with only patients who tested positive for COVID19 using a one-sided test, with a z-score corresponds to the log of the odds-ratio for recovery between the two groups. We will obtain the estimate of the odds ratio, and 95% CI, from logistic regression. As a secondary analysis, we will stratify the analysis, and obtain separate estimates of the odds-ratio by group. However, we are not powered to test the interaction for significance, and we do not expect significance within group.

Interim analysis: We will perform two interim analyses at 34% and 68% completion, testing for early efficacy or futility, using z-score boundaries that follow Hwang-Shih-DeCani alpha spending rules. Following those rules, we have 90% power using 100% of the sample, if scenario is true.

PATCH 3 (Sub-Study 2), Prophylaxis in Health Care Workers: The transmission of SARS-COV-2 from patient to hospital worker depends on many factors including specifics of standard care to prevent transmission, but especially on the number of patients seen at a given hospital or outpatient practice. Across China the reported hospital worker infection rate is 3.8%, but in Wuhan it is reported as 58% at the height of the epidemic. We will use a 10% transmission rate as the null hypothesis (low dose group). In order for HCQ to be considered effective our alternative hypothesis will be a 1% transmission rate. With a 1:1 randomization for the HCQ to control arms we would require a total of 350 health care workers across all participating ProHealth NY and AHN sites. With the placebo group of 175 participants and the high dose HCQ arm of 175 participants, a one-sided z-test ($\alpha=0.05$) comparing the rates in the two groups would have an at least 80% power to detect a significant difference when the difference in the population rates is at least 9%.

The *hypothesis* will be tested using a one-sided test, with a z-score corresponds to the log of the odds-ratio for the rate of transmission between the two groups. We will obtain the estimate of the odds ratio, and 95% CI, from logistic regression.

Interim analysis: We will perform two interim analyses at 25% and 50% completion, testing for early efficacy or futility, using z-score boundaries that follow Hwang-Shih-DeCani alpha spending rules. Following those rules, we have 80% power using 100% of the sample, if our 10% versus 1% scenario is true.

Z-Value Boundaries

Stage	Boundaries		Information Proportion
	Efficacy	Futility	
1	2.9473	-1.2318	0.2500
2	2.5825	-0.2676	0.5000
3	1.6664	1.6664	1.0000

P-Value Boundaries

Stage	Boundaries		Information Proportion
	Efficacy	Futility	
1	0.00160	0.89099	0.2500
2	0.00491	0.60550	0.5000
3	0.04782	0.04782	1.0000

16.2 Analysis of Secondary Endpoints.

Secondary outcomes will be analyzed as summary statistics, with group means, odds-ratios, and 95% CIs. We may conduct exploratory analyses using regression methods appropriate for each type of measure. Tests for significance of estimated parameters will not be reported as we will not be controlling for multiple testing.

PATCH 2 (Sub-Study 1): Rate of secondary infection of housemates is a binomial count by household. We will summarize the proportion or rate by group, with 95% CI. With sufficient data, we will explore subgroups, patient, and secondary patient characteristics using logistic regression. Rate of hospitalization is a binary measure. We will summarize rates by group and estimate the odds-ratio for treatment. Adverse event rates will be summarized as a count by participant, and mean count by group, and we will estimate a rate-ratio for treatment. We will summarize rates by group and estimate the odds-ratio for treatment.

PATCH 3 (Sub-Study 2): Rate of hospitalization is a binary measure. We will summarize rates by group and estimate the odds-ratio for treatment. Adverse event rates will be summarized as a count by participant, and mean count by group, and we will estimate a rate-ratio for treatment. We will summarize the count of shifts missed by group and estimate the rate ratio for treatment.

REFERENCES

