4.0 PARTICIPANT REGISTRATION/PROCEDURES

The following information is to be provided at the time of registration to the trial:

Participant Identification Information for PATCH 2 & PATCH 3:

- Participant initials (first and last)
- Participant's chronic medical problems
- Gender
- Birth date (mm/yyyy)
- Race
- Ethnicity
- Nine-digit ZIP code
- State of residence
- County of residence
- Cell phone number and alternate numbers
- Email address

Participant Identification Information for PATCH 2 Only (Sub-study 1): Identify the number of fulltime inhabitants at the residence where the participant will stay during the 14-day self-quarantine as well as ages and sex of each co-inhabitant and relationship to the study participant.

Participant Procedure for PATCH 2 (Sub-Study 1) (See study process flows)

1. Interested participants self-refer for study by completing online eligibility checklist on study portal (www.patchstudy.com)
2. Review inclusion and exclusion criteria: participant is 50-75 years of age and self-reported as having a fever within the last four days will undergo swab testing for COVID-19 per clinical care guidelines and approach, and then sent home for a self-imposed quarantine
3. Reviews the study and the Informed Consent Form with the subject and obtains informed consent via DocuSign
4. Participant study ID is assigned, and subsequently, randomized into a study arm (HCQ or placebo).
5. Package containing blinded study drug, study journals (medicine log, symptom tracker and experience log) and study documents (details on aims, design, consent forms, and any additional instructions) delivered to address provided by participant as place of residence during period of self-quarantine. Day 1 is defined as the first day the blinded study drug is taken by the participant
6. Lab provides participant's COVID-19 test results to designated Co-PI with designee
7. PI or designee calls participant informing them of result, discussing how to proceed on the trial (if positive, continue taking medication; otherwise, stop) and documenting discussion.
8. Each day, participants will record 1) temperature (to be reported twice daily, either via thermometer or self-report); 2) time medication taken; 3) any symptoms and AEs; and 4) if any co-inhabitants develop symptoms and/or become positive for COVID-19 (confirmed by accepted testing methods)

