9.2 Adverse Events Reporting Period

The study period during which adverse events must be reported is defined as the period from the initiation of the first study treatment to the last administration of study treatment.

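### PATCH 2 adverse events are averaged per participant with no exposure time or split by test result, so early-stopping test-negatives dilute the figure for the 14-day course

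*Combined protocol and SAP*

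**What the plan says.** - **AE summary.** Section 16.2, PATCH 2: "Adverse event rates will be summarized as a count by participant, and mean count by group", "and we will estimate a rate-ratio for treatment". No person-time, offset or split by test result is written.
- **Who counts.** Section 15.1: "All participants will be evaluable for toxicity from the time of their first treatment with HCQ or placebo through final assessment". The restriction to test-positives in Section 16.1 concerns the primary hypothesis, which "will be tested with only patients who tested positive for COVID19". No such limit is given for AEs.
- **How many test negative.** Section 16.1: "We estimate we will need to enroll 500 patients at the time of testing to reach the 100 patients who test positive for COVID19".
- **What negatives do.** In the PATCH 2 procedure of Section 4.0, drug is delivered (step 5), the laboratory reports the result (step 6), and the participant is then called and told how to proceed (step 7): "if positive, continue taking medication; otherwise, stop". Section 7.3 sets the full course at 14 days.
- **AE window.** Section 9.2 defines it as "the period from the initiation of the first study treatment to the last administration of study treatment". Section 15.1 runs toxicity on to the final assessment. The two are not reconciled.

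The time from first dose to test result is not given, and no AE rate is assumed anywhere.

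**The concern.** The AE rate is a named secondary objective of PATCH 2 (Section 1.2), and Section 16.2 reports secondary outcomes as summaries without significance tests. The group mean is therefore the main planned statement about tolerability. As written, it averages full 14-day courses with courses cut short by a negative result, and the plan's own figures make the second kind the large majority of those randomised.

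A reader who takes the mean as the AE burden of 14 days at the study dose would take it as lower than it is. The absolute difference between arms shrinks in the same way, so any excess on HCQ would look smaller per person than for someone who completes the course.

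**Working it through.** **Inputs from the documents.** 500 enrolled and 100 positive (Section 16.1); 14-day course (Section 7.3); 1:1 allocation (synopsis). The evaluable set is everyone dosed (Section 15.1), since Section 16.2 names no set of its own.

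**Assumed.** Negatives take drug for *k* days before stopping, with *k* = 1 to 4. Some share of negatives doses at all. No AE is counted after the last dose, as in Section 9.2.

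**The plan's own figure.** There is no AE figure to reproduce. The 100 positives come from the power statement: 50 per arm, 70% against 95%, one-sided 0.05, at least 90% power. A fixed-design pooled z-test gives 95.9%. With the stated stopping boundaries, power is 94.8% on the pooled z and 89.5% on the log odds ratio. The 100 is thus consistent with the plan, and negatives number 500 − 100 = 400, or 80%.

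**Constant hazard, all negatives dose.** Mean days on drug = (100×14 + 400*k*)/500; factor = 14 / mean.

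**Constant hazard, half the negatives dose.** The other 200 leave the evaluable set. Mean = (100×14 + 200*k*)/300.

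| *k* (days) | All dose: mean days | Factor | Half dose: mean days | Factor |
|---|---|---|---|---|
| 1 | 3.6 | 3.9 | 5.3 | 2.6 |
| 2 | 4.4 | 3.2 | 6.0 | 2.3 |
| 3 | 5.2 | 2.7 | 6.7 | 2.1 |
| 4 | 6.0 | 2.3 | 7.3 | 1.9 |

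If no negative doses, the evaluable set is the 100 positives and the factor is 1.

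**Hazard not constant, all negatives dose.** Pooled mean as a share of the 14-day mean = 0.2 + 0.8·H(*k*)/H(14), where H is the cumulative hazard.

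- Front-loaded, H(x) proportional to 1 − exp(−x/τ). With τ = 5 days the share is 35%, 48%, 58% and 74% at *k* = 1, 2, 3 and 5. With τ = 2 days it is 52%, 71%, 82% and 94%. The factor can therefore fall to about 1.1.
- Rising linearly, H(x) proportional to x². The share is 20%, 22%, 24% and 30% at the same *k*, a larger dilution than under a constant hazard.

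**Absolute difference and rate ratio.** Take assumed rates of 0.10 and 0.05 AEs per day.

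- Constant hazards: the difference over a full course is 0.05×14 = 0.70 per person. Pooled, it is 0.05×3.6 = 0.18 at *k* = 1 and 0.05×6.0 = 0.30 at *k* = 4. The ratio stays at 2.0, because exposure is shortened alike in both arms and cancels.
- HCQ excess growing with time on drug, scaled so that the 14-day ratio is 2.0: cumulative excess = 0.70·(x/14)². At *k* = 3 the pooled excess is (100×0.70 + 400×0.70×9/196)/500 = 0.166, over a background of 0.05×5.2 = 0.26, giving a ratio of 1.64. At *k* = 1 it is 1.79.

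**The case against.** **Negatives may never dose.** The swab is step 2 and delivery step 5 of Section 4.0, and the PATCH 2 job aid (Appendix 3) excludes anyone not yet tested. Some results may arrive before the first dose. This stands, and it is why the half-dosed and none-dosed cases are shown. Against it, treatment starts on receipt of the product (Section 5.0), the kit goes by overnight courier (Appendix 3), and telling positives to continue presupposes that dosing has begun.

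**The longer window in Section 15.1 may govern.** Negatives would then be observed after stopping, and the calculation above counts no such events. The planned mean would pick up off-drug background events, and perhaps late drug effects given the slow kinetics described in Section 7.1a. Time on drug would still differ, so the events due to a full course would still be diluted, by an amount that cannot be computed here.

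**The all-treated mean is a valid summary.** It describes the strategy randomised: start at testing, stop if negative. That is fair, and a reason to keep it alongside. It is not a description of the 14-day course.

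**An offset is unspecified, not excluded.** A rate ratio could carry one, and Section 16.2 allows exploratory regression. The mean count per group does not.

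**Two stronger readings do not hold.** A reader might infer that the rate ratio is pulled towards 1. Under proportional constant hazards it is not. The two weeks to steady state in Section 2.4 was observed in cancer patients and does not show that the AE excess grows over time here. A reader might also infer that safety oversight would be misled. Individual grading, causality review, dose rules and independent medical monitoring (Sections 8.4, 8.5 and 13.0) do not use the group mean.

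**Conclusion.** The point holds as a reporting defect. Followed as written, Section 16.2 yields a mean AE count and an absolute between-arm difference that understate the burden of the 14-day course, provided that some negatives take drug and stop early. The direction follows from the plan's text for on-treatment events; the size does not.

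Under a constant hazard with negatives stopping after 1 to 4 days, the factor is about 3.9 to 2.3 if all dose and 2.6 to 1.9 if half do. Early-clustering AEs make it smaller, a rising hazard makes it larger, and it is 1 if no negative doses. A single large factor should not be quoted as established, because turnaround and the share dosing are both unknown. The rate ratio is affected only if the HCQ excess grows with time on drug. The primary efficacy test is untouched.

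**What to change.** 1. In Section 16.2, tabulate PATCH 2 AEs by arm separately for test-positives, as the main table for the 14-day course, and for test-negatives who took at least one dose. This split is the main remedy, because a person-day rate recovers the 14-day burden only if the hazard is constant.
2. As a supplement, report person-days on treatment and AEs per person-day, and estimate the rate ratio from a Poisson or negative binomial model with log exposure as offset.
3. Reconcile the AE windows in Sections 9.2 and 15.1, and state which one the AE summary uses.
4. Report how many negatives took any drug, and for how long.

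The cost is plan wording: time of medication is already recorded daily (Section 4.0, step 8), and treatment and sample size are unchanged. The downside is precision, since the main table rests on about 50 participants per arm rather than up to 250. The loss in on-treatment time is smaller than those counts suggest. Positives give 50×14 = 700 person-days per arm, and 200 negatives at *k* = 1 to 4 would add 200 to 800. The main table thus keeps 700/900 = 78% to 700/1,500 = 47% of the total. The all-treated summary can be kept alongside.
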